5.4.2 Key secondary analysis

Not applicable.

5.4.3 Secondary analysis

Categorical variables will be analyzed using the logistic model, using the code described above.

Continuous variables will be analyzed using an analysis of covariance (ANCOVA) model with treatment, baseline value, methotrexate usage at baseline (yes, no), and body weight as explanatory variables.

Proc mixed data=aaa order=internal; Class TRT MTX; Model change=TRT MTX BLV weight/ ddfm=kr; Lsmeans TRT/ cl diff; Contrast "sec300 vs plb" TRT 1 0 -1/ cl diff alpha=0.05; Contrast "sec150 vs plb" TRT 0 1 -1/ cl diff alpha=0.05; Run;

For supportive analysis using Cochran-Mantel-Haenszel (CMH) test to compare treatments adjusting for methotrexate usage at baseline, the same code will be used as described above.

5.4.4 Exposure-adjusted incidence rate and 100*(1-α)% confidence interval

It will be assumed that for each of n subjects in a clinical trial the time t_j (j=1,..., n) to the first occurrence of a certain event is observed, or if the event was not experienced, the (censored) time to the end of the observation period. The sequence of first occurrences of an event will be modeled to follow approximately a Poisson process with constant intensity θ . The rate parameter θ will be estimated as $\lambda = D/T$, where $T = \sum t_{j}$ (j=1,..., n) and D is the number of subjects with at least one event. Conditionally on T, an exact 100*(1- α)% confidence interval for a Poisson variable with parameter θ T and observed value D can be obtained based on (Garwood,1936), from which an exact 100*(1- α)% confidence interval for D/T will be derived as follows (Sahai and Anwer, 1993; Ulm, 1990):

Lower confidence limit:

$$L = \frac{0.5c_{\alpha/2,2D}}{T}$$
 for D>0, 0 otherwise,

Upper confidence limit:

$$U = \frac{0.5c_{1-\alpha/2,2D+2}}{T}$$

where $c_{\alpha,k}$ is the α th quantile of the Chi-square distribution with k degrees of freedom.

Novartis	For business use only	Page 58
SAP		Secukinumab/AIN457FUS01

5.4.6 Mixed-effects repeated measures model

Change from baseline in log (hsCRP) will be analyzed using mixed-effects model repeated measures (MMRM) with treatment (3 treatment groups), visit, baseline hsCRP, methotrexate usage at baseline (yes, no), and body weight (kg) as explanatory variables. An unstructured covariance structure will be assumed for this model.

SAS code for mixed model:

proc mixed data=aaa; class TRT USUBJID AVISITN; model CHG=TRT AVISITN WEIGHT BASE / s ddfm=kr; lsmeans TRT*AVISITN / diff cl; repeated AVISITN / type=un subject=USUBJID; run;

In case the MMRM model does not converge the following sequential steps will be used: 1. change ddfm=kr to ddfm=bw. If still no convergence, perform step 2.

2. change type=un to type=cs.

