9.7 Sample size calculation

The sample size was calculated based on the primary efficacy variable (i.e., ACR20 response) for the primary comparison (i.e., secukinumab 300 mg versus placebo). ACR20 response rates of 50% for secukinumab 300 mg and 20% for placebo (corresponding to an odds ratio of 4) at Week 16 were assumed, based on results from AIN457F2312 (FUTURE 2) study. Using a continuity-corrected chi-squared test, an allocation ratio of 2:1, a two-sided significance level of 0.05, and a power of 0.90, approximately 88 patients in secukinumab 300 mg group and 44 patients in placebo group will be needed (nQuery Advisor 7.0). Assuming a loss to follow-up rate of 10% and a 2:2:1 allocation ratio (secukinumab 300 mg: secukinumab 150 mg: placebo), the total number of randomized patients will be approximately 250 (100 on secukinumab 300 mg, 100 on secukinumab 150 mg, and 50 on placebo)

10 Ethical considerations

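### SAP 5.4.6 models change in log(hsCRP) but names untransformed baseline hsCRP as the covariate; taken literally this loses some precision, and naming log baseline instead costs nothing

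*SAP*

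**What the plan says.** SAP 5.4.6 states the model in prose: "Change from baseline in log (hsCRP) will be analyzed using mixed-effects model repeated measures (MMRM) with treatment (3 treatment groups), visit, baseline hsCRP". Methotrexate use at baseline and body weight complete the list. The covariance is also fixed: "An unstructured covariance structure will be assumed for this model".

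The accompanying code has "model CHG=TRT AVISITN WEIGHT BASE / s ddfm=kr". Neither CHG nor BASE is defined there.

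The SAP's other models for continuous outcomes adjust for the baseline of the variable being analysed. SAP 2.7.2 does so for DAS28-CRP and PASDAS, SAP 2.11 for SF-12, and SAP 5.4.3 in its general ANCOVA code.

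The documents give no SD, between-visit correlation, effect size or power target for log hsCRP. It is neither the primary variable nor one of the 12 secondary efficacy variables in SAP 2.7.1.

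**The concern.** Change in log(hsCRP) is log follow-up minus log baseline. If hsCRP is roughly log-normal, this change depends on baseline linearly through log baseline, not through hsCRP itself. A raw, right-skewed covariate captures that relation only in part, and a few very high baselines largely set its slope. The eligibility criteria place no limit on hsCRP, so they do not narrow the range.

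Precision is at stake. Randomization is not stratified (SAP 1.1), so covariate adjustment is the only planned correction for chance differences in baseline against a placebo arm of 50. A covariate on the wrong scale leaves some of that chance variation in the standard error.

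**Working it through.** **Inputs from the documents.** The arm sizes are "100 on secukinumab 300 mg, 100 on secukinumab 150 mg, and 50 on placebo" (protocol 9.7). Protocol Table 6-1 schedules hsCRP at five post-baseline visits up to Week 16 (Weeks 1, 4, 8, 12 and 16).

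**The plan's own figure.** The only design figure is the ACR20 sample size of 88 and 44, for 50% versus 20%. It reproduces:
- Without continuity correction: [1.96·√(1.5×0.4×0.6) + 1.2816·√(0.2×0.8 + 0.5×0.5/2)]² / 0.3² = 38.4, so 39 on placebo.
- With the correction: (38.4/4)·[1 + √(1 + 6/(2×38.4×0.3))]² = 43.3, so 44 on placebo and 88 on 300 mg.
- With 10% loss: 44/0.9 = 48.9 and 88/0.9 = 97.8, rounded up to 50 and 100.

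This confirms the arm sizes but says nothing about hsCRP.

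**Assumptions for the hsCRP check (not in the documents).** Log hsCRP is normal with SD s at baseline and at follow-up, and the correlation between the two is ρ.

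**Step 1: what raw baseline captures.** The squared correlation between hsCRP and log hsCRP is r² = s²/(exp(s²) − 1).
- s = 1.0: 1/(2.718 − 1) = 0.58
- s = 1.2: 1.44/(4.221 − 1) = 0.45
- s = 1.4: 1.96/(7.099 − 1) = 0.32

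**Step 2: residual variance of the change.**
- Adjusted for log baseline: s²(1 − ρ²).
- Adjusted for raw baseline: s²[(1 − ρ²) + (1 − ρ)²(1 − r²)].

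The ratio is 1 + (1 − ρ)(1 − r²)/(1 + ρ).

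**Step 3: excess variance by formula (excess standard error in brackets).**

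| s | ρ = 0.4 | ρ = 0.5 | ρ = 0.7 |
|---|---|---|---|
| 1.0 | 17.9% (8.6%) | 13.9% (6.7%) | 7.4% (3.6%) |
| 1.2 | 23.7% (11.2%) | 18.4% (8.8%) | 9.8% (4.8%) |
| 1.4 | 29.1% (13.6%) | 22.6% (10.7%) | 12.0% (5.8%) |

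Example for s = 1.2, ρ = 0.5: 1 + 0.5×0.553/1.5 = 1.184, and √1.184 = 1.088.

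**Step 4: simulation at 100/100/50.**
- Linear model at one visit with treatment, methotrexate, weight and baseline (2,000 trials per setting; s 1.0 to 1.4, ρ 0.4 to 0.6): variance ratios 1.09 to 1.24.
- Five-visit repeated-measures model with unstructured covariance, treatment-by-visit means and a common baseline slope (1,500 trials per setting): 1.19, 1.10 and 1.07 for s = 1.0, and 1.19, 1.17 and 1.09 for s = 1.2, at ρ = 0.4, 0.5 and 0.7.

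Together these span 1.07 to 1.24. In standard error, √1.07 = 1.034 and √1.24 = 1.114, so about 3 to 11%.

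The simulated maximum (1.24) is below the formula's (1.29) because the realised r² in samples of 250 exceeds the population value. It averages about 0.63, 0.53 and 0.45 at s = 1.0, 1.2 and 1.4. Putting 0.45 into the formula at ρ = 0.4 gives 1 + 0.6×0.55/1.4 = 1.24.

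**Step 5: wider assumptions, by formula.** For s from 0.6 to 1.5 and ρ from 0.3 to 0.8, the excess variance runs from 1.9% to 39.6%. This still assumes equal SDs. If the follow-up SD were 0.8 of the baseline SD, the excess would be (0.8ρ − 1)²(1 − r²)/[0.64(1 − ρ²)], about 24 to 55% for s 1.0 to 1.2 and ρ 0.3 to 0.8.

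**Step 6: bias.** With no true effect, the mean simulated contrast in the repeated-measures model was within 0.007 of zero under both adjustments.

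**The case against.** The strongest objection is that raw scale is not established. BASE sits beside CHG, and SAP 2.8.3 and 2.8.4.2 define change, for laboratory data and vital signs, as post-baseline minus baseline value. Applied here, the baseline of a change in log(hsCRP) is log baseline, and the prose may be loose shorthand for it. SAP 2.13 is also absent from the public text, and it may hold the fuller specification. This stands: the documents do not settle the scale, and the loss is conditional. But the code cannot be relied on to override the prose, because its MODEL statement already departs from it by omitting methotrexate. Two programmers could fit different models from the same section.

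A second objection is that the size rests on assumed values. That also stands, which is why a range is given.

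Three stronger readings are tempting, and the documents do not support them:
- A reader might infer that the contrast is confounded or biased. Treatment is randomized, and the simulation shows no bias under either covariate. Chance imbalance left in one realised estimate is part of its standard error.
- A reader might convert the loss into power points. The documents give no effect size or power target for log hsCRP, so any such figure would follow from an invented effect.
- A reader might take it to weaken the efficacy conclusions. The primary and listed secondary analyses do not use this model.

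**Conclusion.** The point holds as a conditional one about precision. As written, the covariate and the outcome in SAP 5.4.6 are on different scales. If the prose is carried out literally, the variance of each dose versus placebo contrast is about 7 to 24% larger in simulation than with log baseline, or about 3 to 11% in standard error. This assumes log-normal hsCRP, equal SDs of 1.0 to 1.4 at baseline and follow-up, and a correlation of 0.4 to 0.7. Keeping equal SDs but widening the other assumptions gives about 2 to 40% in variance; a smaller SD at follow-up would raise it. If BASE is already log baseline, the loss is zero and only the wording needs correcting. A reader might conclude that the SAP definitely adjusts on the raw scale, but the undefined BASE and the missing section 2.13 do not allow that. This is a free improvement to an analysis outside the primary and listed secondary variables.

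**What to change.** In SAP 5.4.6, replace baseline hsCRP with log(baseline hsCRP) in the prose. Define BASE in the code as the baseline of the same log-transformed variable from which CHG is derived.

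The cost is one word and, at most, one derived variable. No new data are needed and no other analysis changes. If log baseline was always intended, the edit only documents it. The SAP's change table shows updates after the Week 16 database lock, so if this model has already been run, record which scale was used.

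Two separate mismatches in the same code can be settled in the same edit. Methotrexate is in the prose but not in the MODEL statement. By-visit contrasts are requested through "lsmeans TRT*AVISITN / diff cl", although that interaction is not in the MODEL statement, so the code as written cannot produce them.

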Eligible patients will be randomized to secukinumab 300 mg (Group 1), secukinumab 150 mg (Group 2) or placebo (Group 3) for the first 16 weeks (until Week 16 treatment). Note that the treatment groups above for a patient may differ depending on the time period of the analysis and whether one assesses the patient for efficacy or safety.

The analysis will be conducted on all patients' data at Week 16 and at the time the trial ends (Week 52).

For Treatment Period 2, all data analyses will be presented by Weeks 16, 28 and 40, based on the number of patients who switched to secukinumab 300 mg and number of patients who continued in secukinumab 150 mg at the respective visits.

All the assessments from scheduled visits will be included for summaries and analyses, whereas the listing will include available data.

Comparative efficacy data

Comparative efficacy analyses (i.e. inferential efficacy comparisons with placebo) will focus on the time period when both active drug and the placebo are given in a manner suitable for making comparisons (i.e., first 16 weeks of treatment). Comparative efficacy will be performed based on the FAS using the randomized treatment. After week 16 till week 52, the efficacy variables will be summarized descriptively or otherwise specified using inferential analysis, on the FAS.

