2.4 Treatments (study treatment, rescue medication, concomitant therapies, compliance)

2.4.1 Study treatment / compliance

Study Treatment

The summaries by treatment group will be performed cumulatively by the actual treatment received (as follows) for every visit until Week 16.

Treatment groups in Treatment Period 1:

- Secukinumab 300 mg
- Secukinumab 150 mg
- Placebo

For entire treatment period, the summaries by treatment group will be performed cumulatively by the actual treatment received (as follows) for every visits till Week 52, including the patients who switched at Weeks 16, 28, 40.

Treatment groups for entire treatment period analysis:

For efficacy variables:

- Secukinumab 300 mg
- Secukinumab 150 mg 150 mg (R)
- Secukinumab 150 mg 300 mg (NR)
- Any Secukinumab 150 mg
- Placebo Secukinumab 300 mg

For safety variables

- Any Secukinumab 150 mg
- Any Secukinumab 300 mg
- Any Secukinumab

The analysis of study treatment data will be based on the Safety Set. The number of active and placebo injections will be summarized by treatment group up to Week 52.

Duration of exposure

The duration of exposure to study treatment will also be summarized by treatment group. In addition, the number and percentage of subjects with cumulative exposure levels (e.g. any exposure, ≥ 1 weeks, ≥ 2 weeks, ≥ 3 weeks, ≥ 4 weeks, ≥ 8 weeks, etc.) will be presented.

Duration of exposure of study Treatment Period 1 will be defined as the time from first dose of study treatment till the end of Treatment Period 1 (Week 16).

Duration of exposure of switched treatment group (for patients switching from placebo to secukinumab 300 mg, or secukinumab 150 mg to 300 mg) in Treatment Period 2 will be defined as the time from treatment switch to end of Treatment Period 2 (Week 52).

The duration of exposure of initial treatment group in Treatment Period 2 will be defined as the time from first dose (Week 16) till the end of Treatment Period 2 (for secukinumab 300 mg group) or until the switch (for secukinumab 150 mg group).

For patients who discontinue, this will be the patient's last visit in the corresponding treatment period.

Duration of exposure (years) = duration of exposure (days) / 365.25

Duration of exposure (100 patient years) = duration of exposure (years) / 100

The analyses of duration of exposure described above will be done for the entire study treatment periods.

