5.4 Statistical models

5.4.1 Primary analysis

The primary analysis will be performed comparing treatments with respect to the primary

efficacy variable in a logistic regression model with treatment, methotrexate usage at baseline (yes, no), and body weight as explanatory variables.

Proc logistic data=aaa; Class TRT MTX/ param=glm; Model AVAL= TRT MTX weight; Lsmeans TRT / diff cl exp; Ods output diffs=lsm_diff; Run;

Logistic regression will be applied to response variables at each visit.

In cases where logistic regression doesn't converge, Fisher's exact test will be applied for comparisons between AIN457 doses. In this case, no odds ratios or confidence intervals will be estimated, but p-values may be calculated.

Proc freq data=aaa; Table TRT * AVAL / fisher; Where TRT in ("AIN457 xx mg" "Placebo"); Run;

In cases where separation is a concern, e.g. 0% response in one treatment (sub) group, an exact logistic regression model will be applied. Proc logistic data=aaa exactonly; Class TRT MTX / param=glm; Model AVAL = TRT MTX weight; Exact TRT / estimate;

Ods output exactoddsratio=exactoddsratio;

Run;

For supportive analysis using Cochran-Mantel-Haenszel (CMH) test to compare treatment adjusting methotrexate usage at baseline, the following code will be used.

proc freq data=aaa; tables TRT*MTX / cmh; run;

where AVAL= dependent variable TRT= Treatment MTX= Methotrexate usage at baseline Weight= body weight

Multiple Imputation

A multiple imputation will be performed based on MAR with treatment (3 treatment groups), methotrexate usage at baseline (yes, no), and body weight (in kg) as explanatory variables of primary efficacy variable (ACR20 response) for visits up to the primary time point (Week 16) using Markov Chain Monte Carlo (MCMC) method with EM algorithm.

Impute the missing values 100 times (NIMPUTE) with a seed=457<studycode> as shown below:

proc mi data= min= max= out=imp minmaxiter=10000000 nimpute=100 seed=457;

by trt;

var weight_base mtxuse_base var1_week1-var1_week16;

mcmc chain=multiple initial=em;

run;

Where var1 is the 1st component of ACR and this step will be repeated for every components of ACR, e.g., as follows:

proc mi data=imp min=<min of scale> max=<max of scale> out=imp2 minmaxiter=10000000 nimpute=100 seed=457;

by trt _imputation_; var weight_base mxtuse_basevar2_week1-var2_week16; mcmc chain=multiple initial=em;

run;

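### The repeated-measures model for log(hsCRP) requests treatment-by-visit means without a treatment-by-visit term, and its code drops the methotrexate covariate that its prose lists

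*SAP*

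**What the plan says.** SAP 5.4.6 describes a repeated-measures model for change from baseline in log(hsCRP) with unstructured covariance.

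- **Prose:** the model is fitted "with treatment (3 treatment groups), visit, baseline hsCRP, methotrexate usage at baseline (yes, no), and body weight (kg) as explanatory variables". No interaction is mentioned.
- **CLASS statement:** "class TRT USUBJID AVISITN". Methotrexate is not there.
- **MODEL and LSMEANS statements:** "model CHG=TRT AVISITN WEIGHT BASE / s ddfm=kr; lsmeans TRT*AVISITN / diff cl". MODEL has neither methotrexate nor a treatment-by-visit term, while LSMEANS names that term.
- **Non-convergence steps:** the first changes the degrees-of-freedom method and the second is "change type=un to type=cs". The mean model stays as it was.

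Elsewhere the SAP's code does carry methotrexate: the logistic code in 5.4.1 has "Class TRT MTX/ param=glm; Model AVAL= TRT MTX weight" and the ANCOVA code in 5.4.3 has "Class TRT MTX; Model change=TRT MTX BLV weight/ ddfm=kr".

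**The concern.** The section describes two different targets. Prose and MODEL define one treatment effect pooled over visits; LSMEANS asks for a separate effect at each visit. Whoever programs the analysis has to choose between them. Because the trial is organised around Week 16, a pooled difference could be taken for the Week 16 effect. If the effect on hsCRP builds up over time, that figure would be too small at Week 16 and too large at Week 1.

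The methotrexate mismatch is smaller. Treatment is randomised, so leaving the covariate out costs a little precision, but the fitted model would not be the one described.

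**Working it through.** **1. What the mean model allows.** Table 6-1 of the protocol schedules post-baseline hsCRP at Weeks 1, 4, 8, 12 and 16 in Treatment Period 1. The written model, covariates aside, is

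E[change | arm a, visit v] = μ + α_a + β_v

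so the drug-minus-placebo contrast at visit v is α_drug − α_placebo, which does not depend on v. The five visit contrasts are one and the same vector (rank 1). By count: 3 arms × 5 visits = 15 cell means are requested; the model has 1 + 2 + 4 = 7 treatment and visit parameters; the missing 2 × 4 = 8 are the interaction.

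**2. What the additive estimate converges to.** With free visit means and covariance Σ, generalised least squares gives

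δ̂ = (1′Σ⁻¹δ) / (1′Σ⁻¹1)

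where δ is the vector of true visit effects. Under compound symmetry the weights are equal and δ̂ is the plain average. The documents give no hsCRP effects, SD or correlations, so everything here is assumed: SD 1, a 300 mg effect of −0.70 at Week 16, and the planned 100/100/50 arms. By hand, under compound symmetry:

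- Moderate (−0.30, −0.55, −0.65, −0.70, −0.70): sum 2.90, mean 0.58; 0.58/0.70 = 0.829.
- Gradual (−0.10, −0.25, −0.45, −0.60, −0.70): sum 2.10, mean 0.42; 0.42/0.70 = 0.600.
- Near-linear (−0.04, −0.18, −0.35, −0.53, −0.70): sum 1.80, mean 0.36; 0.36/0.70 = 0.514.

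The ratios below cover four correlation structures (compound symmetry 0.3 and 0.6; AR(1) 0.6 and 0.8 per 4 weeks), with the misfit fed back into the unstructured covariance. Coverage is from 2,000 simulated trials per cell, with a 150 mg effect 0.85 of the 300 mg effect, no dropout and no covariates.

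| Onset | Additive estimate ÷ Week 16 effect | Coverage of Week 16 effect by additive 95% CI | Coverage of Week 1 effect |
|---|---|---|---|
| Flat from Week 1 | 1.00 | 94–95% | 94–95% |
| Moderate | 0.76–0.83 | 77–85% | 33–64% |
| Gradual | 0.59–0.60 | 33–50% | 20–42% |
| Near-linear | 0.51–0.53 | 18–38% | 21–41% |

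With the interaction in the model, Week 16 coverage is 94–96% throughout.

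**3. One cell checked by hand** (compound symmetry 0.6, moderate onset). The visit-specific SE is √(1/100 + 1/50) = √0.03 = 0.173. The pooled SE is √(0.03 × (1 + 4 × 0.6)/5) = √0.0204 = 0.143. At Week 16 the bias is 0.70 − 0.58 = 0.12, or 0.84 SE, so coverage is about Φ(1.12) − Φ(−2.80) = 87%. The simulation gave 85%, with SE 0.142. At Week 1 the bias is 0.58 − 0.30 = 0.28, or 1.96 SE, giving about 50%; the simulation gave 51%.

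**4. Methotrexate.** The SE inflation from omitting a covariate with partial R² is √(1/(1 − R²)). For assumed R² of 0, 0.01, 0.02 and 0.05 this is 1.000, 1.005, 1.010 and 1.026.

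**The case against.** **The code would probably fail visibly.** PROC MIXED expects an LSMEANS effect to be in MODEL, so the likely outcome is an error and not a pooled number labelled Week 16. The LSMEANS line also shows that visit-specific output was wanted, so the natural repair is the one proposed below. This is a fair point (the code was not run in SAS here). It makes the bias a conditional risk. It does not make the section consistent, because the prose lacks the interaction too and repairing the code alone would leave it contradicting the prose.

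**The figures rest on assumed onset patterns.** This also stands. Protocol 3.6 reports clinical benefit within the first one to three weeks in earlier trials. That is not specific to hsCRP and does not establish a plateau, but it favours the upper rows of the table: from flat to moderate onset the ratio is 0.76 to 1.00 and Week 16 coverage 77 to 95%. The simulation also leaves out dropout, covariates and the Kenward-Roger adjustment.

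**SAP 2.13 is not in the public text.** The SAP's revision table cites it, and it may say more about hsCRP, including which time points matter. It could settle which target was intended. It could not make the statements in 5.4.6 agree with one another.

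**The methotrexate omission is clerical.** Agreed; it is included because the same edit corrects it.

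**Conclusion.** The concern holds. SAP 5.4.6 contradicts itself on the treatment-by-visit term and on methotrexate, and both follow from the text without any assumption. The mean model as specified allows only one drug-placebo difference across visits.

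The numerical consequence is conditional. It arises only if the additive model is fitted and its estimate is read as a Week 16 effect, and its size depends on the assumed onset: none if the effect plateaus by Week 1, up to roughly half the Week 16 effect if onset is near-linear.

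Severity is low. Change in log(hsCRP) is not the primary variable and is not among the 12 secondary variables in SAP 2.7.1. The ACR20 analysis and the sample size are untouched.

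**What to change.** In SAP 5.4.6, add the treatment-by-visit interaction to the list of model terms in the prose and change two code lines:

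`class TRT AVISITN MTX USUBJID;`

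`model CHG = TRT AVISITN TRT*AVISITN BASE MTX WEIGHT / s ddfm=kr;`

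Keep the LSMEANS line. State that placebo comparisons are reported through Week 16. This agrees with SAP 2.1, where "Comparative efficacy analyses (i.e. inferential efficacy comparisons with placebo) will focus on the time period when both active drug and the placebo are given", and with the three arms that SAP 2.4.1 lists under "Treatment groups in Treatment Period 1". If a visit-pooled effect was in fact intended, say so and request LSMEANS for TRT alone; the methotrexate correction applies either way.

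The drafting cost is one phrase and two lines. The statistical cost is precision: the simulated SE of the Week 16 difference is 22% larger than the pooled SE under compound symmetry 0.6 (0.173 against 0.142), and 20 to 52% larger over the four correlation structures. That is the price of estimating the effect at a stated visit.
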